5.3.3 Reasons for Withdrawal and Discontinuation of Vaccinations

Subjects are free to withdraw from the study at any time and for any reason. Subjects who have received vaccine, regardless of the number of doses received, or who developed an AE or SAE will be encouraged to remain in the study to be followed for safety purposes.

Subjects may voluntarily withdraw their consent for study participation at any time and for any reason, without penalty.

A subject may withdraw or be withdrawn from the study for any of the following reasons:

- Medical disease or condition, or any new clinical findings for which continued participation, in the opinion of the Principal Investigator or appropriate co-investigator, would compromise the safety of the subject, or would interfere with the subject's successful completion of the study, or would interfere with the evaluation of responses.
- Subject no longer meets eligibility criteria.
- As deemed necessary by the Principal Investigator or appropriate co-investigator for noncompliance or other reasons.
- Subject withdrawal of consent.
- Subject lost to follow-up.
- Termination of the study.
- New information becomes available that makes further participation unsafe.

The second or third study vaccination may not be administered to a subject if any of the following criteria are met:

-
- Medical condition (including pregnancy) for which continued participation, in the opinion of the Principal Investigator or appropriate co-investigator, would pose a risk to the subject or would be likely to confound interpretation of the results.
 - Presence of signs or symptoms that could confound or confuse assessment of study vaccine reactogenicity. For subjects with injection site or systemic signs or symptoms, or with an acute illness, including an oral temperature greater than 38.0°C, the study vaccination should/may be postponed/deferred until signs, symptoms, or acute illness have resolved and if within the acceptable protocol-specified window for that visit. If outside this window, the Sponsor must first approve the second or third study vaccination and the documentation of approval should be filed in the subject's chart.

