 - Any unresolved or continuing solicited or unsolicited Grade 3 adverse event. An unresolved or continuing Grade 1 or Grade 2 adverse event is permissible unless, in the opinion of the Principal Investigator or appropriate co-investigator, it would render study vaccination unsafe or interfere with the evaluation of responses.
 - Grade 3 clinical safety laboratory value that does not decrease to Grade 2 or less prior to the second or third study vaccination. Any clinical safety laboratory parameter may be re-evaluated only once at the central (clinical) laboratory prior to the second or third study vaccination. If the clinical safety laboratory value decreases to Grade 2 or less, the subject may receive the second or third study vaccination. The second or third study vaccination should be scheduled to occur within the acceptable protocol-specified window for that visit. If outside this window, the Sponsor must first approve the study vaccination and the documentation of approval should be filed in the subject's chart.
 - Severe or sustained reaction or disability related to the first study vaccination.
 - New onset of illness or condition that meets exclusion criteria.
 - Subject no longer meets eligibility criteria.
 - As deemed necessary by the Principal Investigator or appropriate co-investigator for noncompliance or other reasons.
 - Subject refusal of further study vaccination.
 - Subject withdrawal of consent.
 - Subject lost to follow-up.
 - Termination of the study.
 - New information becomes available that makes further participation unsafe.

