9.2 Methods and Timing for Assessing, Recording, and Analyzing Safety Parameters

9.2.1 Adverse Events

An adverse event (AE) includes any noxious, pathological or unintended change in anatomical, physiological or metabolic functions as indicated by physical signs, symptoms and/or laboratory-detected changes occurring in any phase of the clinical study, whether associated with the study vaccine or placebo, and whether or not considered vaccination related. This includes an exacerbation of pre-existing conditions and intercurrent illnesses.

All AEs will be graded for severity and relationship to study vaccine. A study clinician will be readily available for the duration of the trial to assess AEs. Should a subject call on a study clinician to report an AE, it will be fully documented in their study chart, and discussed with the Principal Investigator.

All AEs will be assessed by the investigator using the following protocol-defined grading system, as or described in Tables 2-5:

Grade 1:	Mild - No effect on activities of daily living; no medical intervention/therapy required
Grade 2:	Moderate - Partial limitation in activities of daily living (can complete $\geq 50\%$ of baseline); no or minimal medical intervention/therapy required
Grade 3:	Severe - Activities of daily living limited to $< 50\%$ of baseline; medical evaluation/therapy required

All AEs will have their possible relationship to study vaccine assessed using the following terms:

Definite:	Clear-cut temporal association, and no other possible cause.
Probable:	Clear-cut temporal association and a potential alternative etiology is not apparent.
Possible:	Less clear temporal association; other etiologies also possible.
Unlikely:	Temporal association between the AE and the vaccine or the nature of the event is such that the vaccine is not likely to have had any reasonable association with the observed illness/event (cause and effect relationship improbable but not impossible).
Not Related:	The AE is completely independent of vaccine administration; and/or evidence exists that the event is definitely related to another etiology.

The degree of certainty with which an AE can be attributed to administration of study vaccine will be determined by how well the event can be understood in terms of one or more of the following:

1. The event being temporally related with vaccination or reproduced on re-vaccination.

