9.2.3 Serious Adverse Events

An SAE is an AE, whether considered related to a study vaccine or not, meeting one of the following conditions:

1. Death during the period of protocol-defined surveillance
2. Life threatening: defined as an event that places a subject at immediate risk of death at the time of the event and does not refer to an event that hypothetically might have caused death were it more severe
3. Hospitalization during the period of protocol-defined surveillance: defined as at least an overnight stay in the hospital or emergency ward for treatment that would have been inappropriate if administered in the outpatient setting
4. Results in a congenital anomaly or birth defect
5. Results in a persistent or significant disability or incapacity: defined as a substantial disruption of the study subject's ability to carry out normal life functions
6. Any other important medical event that may not result in death, be life threatening, or require hospitalization, may be considered a serious AE when, based upon appropriate medical judgment, the event may jeopardize the subject and may require medical or surgical intervention to prevent one of the outcomes listed above.

9.2.4 Procedures to be Followed in the Event of Abnormal Laboratory Test Values or Abnormal Clinical Findings

The Principal Investigator or appropriate co-investigator is responsible for reporting all AE/SAEs that are observed or reported during the study, regardless of the relationship to study products. AE/SAEs, abnormal clinical laboratory test values, or abnormal clinical findings will be documented, reported, and followed appropriately.

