The study will be double-blinded until all study subjects have completed their Day 140 visit, after which the Sponsor and investigators will be unblinded. During the double-blinded part of the study, a study subject's randomization code may be unblinded only for safety purposes. This is unlikely to occur, since once a vaccine is administered, knowing which vaccine was given is unlikely to influence the medical management of an AE. This procedure is therefore exceptional and any decision to unblind will be discussed with the sponsor, the Principal Investigator, the Independent Safety Monitor, and the SMC. If deemed necessary for urgent safety reasons, the Independent Safety Monitor, in consultation with the SMC (if possible in a timely manner), may unblind a specific subject without revealing the study blind to the investigators or the Sponsor. Any unblinding will be thoroughly documented. It is to be emphasized that the Independent Safety Monitor may put the study on hold at any time and discuss with the SMC. In the event that the investigators come to know the study code prior to final unblinding, the Principal Investigator must notify the Sponsor immediately. The reasons will be documented by the Principal Investigator and added to the study file.

The decision to completely unblind the study prior to Day 140 or permanently stop the study prior to Day 380 will take the form of a formal recommendation by the SMC to the study Sponsor. The Principal Investigator must then notify the IRBs of this decision.

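### The past-reaction criterion for withholding a dose (Protocol 5.3.3) names only the first vaccination, so a resolved severe or sustained reaction to dose 2 may meet no fixed rule before dose 3

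*Protocol*

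**What the plan says.** The list in Protocol section 5.3.3 opens with "The second or third study vaccination may not be administered to a subject if any of the following criteria are met", so it governs both later doses. Three of its items concern reactions or abnormal findings at a stated grade or duration:

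- Past reaction: "Severe or sustained reaction or disability related to the first study vaccination".
- Grade 3 adverse event: "Any unresolved or continuing solicited or unsolicited Grade 3 adverse event".
- Grade 3 laboratory value: "Grade 3 clinical safety laboratory value that does not decrease to Grade 2 or less prior to the second or third study vaccination".

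A further item asks whether signs or symptoms are present that could confuse the assessment of reactogenicity; it leads to deferral until they clear. The discretionary items are a medical condition that the investigator judges risky, a general clause for whatever the investigator deems necessary, and "New information becomes available that makes further participation unsafe".

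Section 9.2.1 labels Grade 3 as severe: "Severe - Activities of daily living limited to" less than half of baseline. Section 9.2.3 counts among serious adverse events one that "Results in a persistent or significant disability or incapacity". Section 9.5 sets the halting rules and adds that "the Independent Safety Monitor may put the study on hold at any time and discuss with the SMC".

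**The concern.** A rule for re-dosing should be at least as strict about the most recent dose as about an earlier one. Here the only item that looks back at a reaction already over stops at dose 1, although the list applies equally to dose 3. The neighbouring laboratory item names both later doses, and the protocol gives no reason for the narrower wording.

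For some dose-2 reactions, then, whether dose 3 is given depends on individual judgment, where the sponsor wrote a criterion for the same reaction to dose 1. Section 6.3 allows no dose modification, so the subject receives the full third dose or none. The safety reports that section 9.6.2 requires before Groups 3 and 5 need cover only 14 days after the first vaccination, so no scheduled report is tied to dose 2 before dose 3 is given.

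**Working it through.** **Step 1: which rules catch a dose-2 reaction?** Take one subject whose reaction to dose 2 was severe or sustained, has resolved, and was neither allergic nor serious.

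| Rule | Does it apply before dose 3? |
|---|---|
| 5.3.3, past reaction | No: first vaccination only |
| 5.3.3, signs or symptoms present | No: tests current status |
| 5.3.3, Grade 3 adverse event | No: must still be ongoing |
| 5.3.3, Grade 3 laboratory value | No, once back at Grade 2 or lower |
| 5.3.3 through 5.2, exclusion 16 | No: severe allergy or anaphylaxis only |
| 9.5, related SAE, AESI or Grade 3 hypersensitivity in one subject | No, by construction |
| 9.5, one objective or laboratory Grade 3 finding, at least probably related | Not for a subjective symptom; erythema or swelling alone is exempt |
| 9.5, same Grade 3 clinical event in one Group | Needs two subjects |
| 5.3.3 discretionary items; 5.2, exclusion 12; safety monitor or SMC | Possible, but by judgment |

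Three kinds of event pass through: one subject's Grade 3 pain, headache or myalgia; Grade 3 erythema or swelling alone in one subject; and a prolonged lower-grade clinical reaction that has cleared. Disability is not among them: it is an SAE and, if related, suspends vaccination under 9.5.

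**Step 2: would such a reaction be over by dose 3?** Section 7.3 places dose 2 at Day 56 ± 7 (Days 49 to 63) and dose 3 at Day 112 ± 14 (Days 98 to 126).

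- Shortest interval: 98 − 63 = 35 days.
- Nominal interval: 112 − 56 = 56 days.
- Longest interval: 126 − 49 = 77 days.

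A reaction that ends within the 14-day solicited period therefore ended at least 35 − 14 = 21 days before dose 3 and no longer counts as ongoing.

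**Step 3: how often?** The protocol gives no rate. As an assumption, apply the true rates p = 0.5%, 1%, 3% and 5% from the table in section 11.2 to one type of Grade 3 symptom after dose 2, with all 60 subjects receiving dose 2.

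- Expected subjects: 60p.
- Chance of at least one: 1 − (1 − p)^60. This reproduces the N=60 column of that table (25.97%, 45.28%, 83.92%, 95.39%).
- Among Groups of 10 with any such event, the share with exactly one: 10p(1 − p)^9 / [1 − (1 − p)^10].

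| p | Expected of 60 | At least one of 60 | Exactly one, given any in a Group |
|---|---|---|---|
| 0.5% | 0.3 | 26.0% | 97.8% |
| 1% | 0.6 | 45.3% | 95.5% |
| 3% | 1.8 | 83.9% | 86.9% |
| 5% | 3.0 | 95.4% | 78.5% |

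For p = 1%, the last column is 0.0914 / 0.0956 = 95.5%. It counts dose 2 only. The two-subject rule in 9.5 has no per-dose limit, so a matching event after another dose could also trigger it; these shares are upper figures for how often the rule stays silent. Section 2.1.9 reports mostly mild-to-moderate local reactions so far, which points to the low end of the rates.

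**The case against.** The strongest reply is that nobody is obliged to give dose 3. The investigator can withhold it under several items, the safety monitor and SMC can recommend suspension for one subject, and the monitor can put the study on hold. That stands, and it limits the consequence. It does not explain the wording, because the same discretion exists after dose 1 and the sponsor still wrote a criterion there.

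A second reply concerns the word severe. If it meant any Grade 3 event, the separate item on ongoing Grade 3 events would add nothing for a related dose-1 event. The laboratory item likewise permits re-dosing once the value improves. A graver meaning may be intended, and most graver dose-2 events are covered elsewhere. That reading stays open, although the label in 9.2.1 supports the broader one. The sustained branch does not depend on it, but what remains there is modest: a cleared lower-grade reaction, when 5.3.3 permits dosing even during a continuing Grade 1 or 2 event unless the investigator objects.

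Third, neither severe nor sustained is tied to a grade or duration in this item, so judgment enters after dose 1 too, and the correction does not remove it. That is fair: the change makes the two doses consistent and does not sharpen the terms.

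Finally, the assumed rates come from a generic table and are not reduced for events that are unrelated, unresolved or acted on by the investigator. They show a range of possibilities and do not estimate the frequency of the gap.

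**Conclusion.** The criterion is wrong as written and minor in weight. Section 5.3.3 is laxer about the second vaccination than about the first, without a stated reason, and no other fixed rule in 5.2, 5.3.3 or 9.5 covers the remaining events. For sustained reactions this follows from the text alone. For severe reactions it also requires reading severe as Grade 3. How many subjects would be affected cannot be stated from the protocol; the 0.3 to 3.0 of 60 rests entirely on the assumed rates. The likeliest explanation is a drafting slip. Sample size, error rates and planned analyses are untouched.

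**What to change.** In the past-reaction item of section 5.3.3, replace *the first* with *a previous*, so that it covers a severe or sustained reaction or disability related to a previous study vaccination. This keeps whatever meaning the sponsor gives to severe and sustained and applies it to both earlier doses. If a different rule after dose 2 is intended, section 5.3.3 should state it and give the reason.

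The edit is two words. Its possible price is a few more withheld third doses, each of which would leave 1 of the 5 subjects in that arm with an incomplete schedule at the Day 126 antibody assessment.

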5.3.4 Handling of Withdrawals

The primary reason for withdrawal from the study will be recorded on the appropriate data collection form. Subjects will be encouraged to complete the Early Termination Visit. The Early Termination Visit procedures are listed in **Section 7.5**. Although subjects are free to withdraw at any time or may be withdrawn by the Principal Investigator or appropriate co-investigator at any time, subjects who receive at least one dose of study vaccines will be encouraged to remain in the study for follow-up safety assessments and collection of venous blood samples for immunogenicity testing. Every attempt will be made to follow all adverse events, including solicited injection site and systemic reactions, serious adverse events, and new-onset chronic medical conditions ongoing at the time of early withdrawal to resolution.

In the case of subjects who fail to appear for a follow-up safety assessment, extensive effort (i.e., three documented contact attempts via in-person visits to the subject's home, made on separate occasions) will be made to locate or recall them, or at least to determine their health status. These efforts will be documented in the subject's records.

5.3.5 Termination of Study

If a dose of vaccine is considered significantly reactogenic (see Section 9.2.2), dose escalation and/or additional vaccinations will be suspended until reviewed by the Independent Safety Monitor, SMC, and study sponsor. Any recommendation of the Independent Safety Monitor, DMID Medical Monitor, and SMC to resume or suspend further injections (either for an individual subject or an entire dose Group) will be communicated in writing to the sponsor and Principal Investigator. All communications from the SMC will subsequently be forwarded by the investigators to the applicable IRBs.

6 STUDY INTERVENTIONS/INVESTIGATIONAL PRODUCTS

Investigators will receive the current versions of the Clinical Investigator's Brochures for *Na*-GST-1/Alhydrogel[®] and *Na*-APR-1 (M74)/Alhydrogel[®], which comprehensively describe all available preclinical and human experience with the experimental vaccines. If relevant new information becomes available during the course of the trial, the investigators will receive the revised Investigator's Brochure(s).

6.1 Study Product Description

6.1.1 Acquisition

Vials of *Na*-GST-1/Alhydrogel[®], *Na*-APR-1 (M74)/Alhydrogel[®], GLA-AF, and sterile saline for injection for this study will be supplied to the study site by the Sabin Vaccine Institute. *Na*-GST-1/Alhydrogel[®], *Na*-APR-1 (M74)/Alhydrogel[®], GLA-AF, and the sterile saline placebo will be transported to the study site at 0.5°C to 10°C; temperature recording devices will accompany the vaccines at all times during transport to ensure temperature limits have not been violated.

6.1.2 Formulation, Packaging, and Labeling

6.1.2.1 *Na*-APR-1 (M74)/Alhydrogel[®]

Na-APR-1 (M74)/Alhydrogel[®] is supplied as a sterile milky-white suspension (when shaken slightly). Each 2.0 ml vial contains a 0.1 mg/ml suspension of *Na*-APR-1 (M74) adsorbed to 0.8 mg/mL of Alhydrogel[®] in a solution containing 10 mM imidazole, 150 mM sodium chloride and 0.3% Empigen BB, with pH 7.4 ± 0.1. The maximum dose that will be administered is 100 µg of *Na*-APR-1 (M74), or 1.0 ml of the final drug product. This volume contains the equivalent of approximately 400 µg aluminum. Lower doses of *Na*-APR-1 (M74) are delivered by injecting smaller volumes of the 0.1 mg/ml suspension: for example, 0.3 ml will be injected to deliver 30 µg *Na*-APR-1 (M74). For all doses, the ratio of *Na*-APR-1 (M74) to Alhydrogel[®] will therefore remain constant: for the 30 and 100 µg doses of *Na*-APR-1 (M74) the respective amounts of Alhydrogel[®] will be 240 and 800 µg (corresponding to approximately 120 and 400 µg aluminum, respectively). *Na*-APR-1 (M74) protein expression was completed at Fraunhofer Center for Molecular Biotechnology (FhCMB/Newark, DE) and purification and vialing at the Walter Reed Army Institute of Research (WRAIR/[name]). The product conforms to established requirements of purity, sterility, safety, and identity.

6.1.2.2 *Na*-GST-1/Alhydrogel[®]

Na-GST-1/Alhydrogel[®] is supplied as a sterile milky-white suspension (when shaken slightly). Each 2.0 ml vial contains 1.35 ml of a 0.1 mg/ml suspension of *Na*-GST-1 adsorbed to 0.8 mg/ml of Alhydrogel[®] in a buffer consisting of 10% glucose and 10 mM imidazole, pH 7.4.

Glucose acts as an excipient and imidazole as the buffer based on evidence that these components specifically enhance the stability and solubility of *Na*-GST-1. The dose that will be administered in this study is 100 µg of *Na*-GST-1, or 1.0 ml of the final drug product. This volume contains the equivalent of approximately 400µg aluminum. *Na*-GST-1/Alhydrogel[®] was manufactured, formulated and vialled at Aeras Global Vaccine Foundation (Rockville, Maryland, USA).

6.1.2.3 Glucopyranosyl-Lipid A Aqueous Formulation (GLA-AF)

GLA-AF will be supplied to the trial site as a 0.5 mL aqueous solution in multi-dose vials containing 25 µg/mL of GLA without preservative. Appropriate volumes of GLA-AF will be withdrawn from the multi-dose vials using a syringe and added to a vial containing *Na*-APR-1 (M74)/Alhydrogel[®], or vice versa (described in the Investigator's Brochure). The mixture must be administered not more than 24 hours after mixing the GLA-AF with *Na*-APR-1 (M74)/Alhydrogel[®].

6.1.2.4 Saline Placebo

Sterile isotonic (0.9%) sodium chloride solution ("normal saline") for injection, U.S. Pharmacopeia (USP), will be procured and shipped to the study site at ambient temperature. Normal saline is a clear liquid. In study subjects randomized to receive *Na*-APR-1 (M74) without co-administered *Na*-GST-1, normal saline will be administered intramuscularly as placebo in an equal volume to the *Na*-APR-1 (M74). It will be administered in the deltoid muscle of the arm opposite to the one in which the *Na*-APR-1 (M74) is delivered so that all study subjects receive two injections on each day of vaccination, thus maintaining the study blind.

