5.3.2 Masking Procedures

Due to the staggered, dose-escalation design of the trial, it will not be possible to blind to *Na*-APR-1 (M74)/Alhydrogel[®] dose assignment or GLA-AF co-administration assignment. That is, those subjects enrolled into Group 1 will receive either 10µg *Na*-APR-1 (M74)/Alhydrogel[®] administered to one arm and sterile saline administered to the alternate arm, or 10µg *Na*-APR-1 (M74)/Alhydrogel[®] in one arm and 100µg *Na*-GST-1/Alhydrogel[®] administered to the alternate arm. Subjects enrolled into Group 2 will receive either 10µg *Na*-APR-1 (M74) /Alhydrogel[®] plus 5µg GLA-AF administered to one arm and sterile saline administered to the alternate arm, or 10µg *Na*-APR-1 (M74) /Alhydrogel[®] plus 5µg GLA-AF in one arm and 100µg *Na*-GST-1/Alhydrogel[®] administered to the alternate arm, and so on.

Investigators and subjects will be blinded to the within-Group random allocation to receive co-administered sterile saline or *Na*-GST-1/Alhydrogel[®] until all subjects have completed their Day 140 visit, the safety and secondary immunogenicity outcomes (i.e., anti-*Na*-GST-1 and anti-*Na*-APR-1 (M74) IgG antibody results by ELISA) have been monitored and entered into the database, and the database has been “soft-locked” for interim analysis. Procedures to maintain blinding include administering two injections to all subjects at each vaccination point. For this, sterile saline will be co-administered to those subjects randomized to receive *Na*-APR-1 (M74) without co-administration of *Na*-GST-1.

The study vaccine manager will also prepare all investigational product doses (vaccine or sterile saline placebo) in a separate room, and will hand filled syringes to the vaccinator(s). Since the 10 and 30µg doses of the *Na*-APR-1 (M74) formulations are of different volumes (0.1 and 0.3ml, respectively for administration without GLA-AF) than that of *Na*-GST-1, the contents of all syringes will be disguised using opaque tape. As a further precaution, the vaccinator(s) will not be involved in assessments of reactogenicity or adverse events.

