Investigators will be unblinded after all subjects have had their study Day 140 visit. After this point, the study will be single-blinded (i.e., subjects will remain blinded to what products they received). The principal justification for unblinding the investigators before the final study visit has been completed is that the safety and immunogenicity data acquired during the vaccination phase of the study will be crucial in guiding the human hookworm vaccine clinical development plan, and we feel that to make an informed decision as to whether or not to proceed to pediatric trials, we must first assess the unblinded data in a timely fashion.

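### Saline placebo volume is matched to the open Na-APR-1 injection, not to the 1.0 ml Na-GST-1 injection it masks, so second-arm volume differs by allocation in Groups 1-4 (40 of 60 subjects)

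*Protocol*

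**What the plan says.** Section 5.3.2 states that Na-APR-1 dose and GLA-AF assignment cannot be blinded. What is masked is the second arm: "Investigators and subjects will be blinded to the within-Group random allocation to receive co-administered sterile saline" or Na-GST-1. Investigators are unblinded once all subjects have had the Day 140 visit, but after that "subjects will remain blinded to what products they received".

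Section 6.1.2.4 sets the placebo rule: "normal saline will be administered intramuscularly as placebo in an equal volume to the *Na*-APR-1 (M74" product, given in the opposite arm "so that all study subjects receive two injections on each day of vaccination, thus maintaining the study blind". No other section fixes a saline volume. Section 6.2 leaves both the volume and the syringe size at whatever is appropriate.

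The Protocol Summary (Description of Interventions, item b) and section 6.1.2.2 fix Na-GST-1 at 100 µg in 1.0 ml for every Group.

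Section 5.3.2 lists the masking measures. "Procedures to maintain blinding include administering two injections to all subjects at each vaccination point". Doses are prepared in a separate room. The section recognises that the 10 and 30 µg Na-APR-1 doses have "different volumes (0.1 and 0.3ml, respectively for administration without GLA-AF") from Na-GST-1, and for that reason "the contents of all syringes will be disguised using opaque tape". In addition, "the vaccinator(s) will not be involved in assessments of reactogenicity or adverse events".

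**The concern.** A placebo protects a blind when it resembles the product it replaces. Here saline replaces Na-GST-1, but its volume follows Na-APR-1, whose identity and dose everyone already knows. In Groups 1-4 a saline subject receives two small injections of equal volume, while a co-administered subject receives one small injection and one of 1.0 ml. The pattern repeats at all three vaccinations, and each subject can compare one arm with the other.

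Safety and reactogenicity are the primary objective. The first hypothesis in section 11.1 is that co-administration does not add reactogenicity, which is the masked contrast. Sections 11.3.1 and 11.4 compare the proportion with at least one injection-site AE by co-administration status, and section 11.4 specifies Fisher's exact test. If subjects can work out their allocation, the reactions that depend on their own account are open to reporting bias. The interim data also feed the decision on paediatric trials (sections 2.2.3 and 5.3.2).

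**Working it through.** **Inputs.** Na-APR-1 and Na-GST-1 are both at 0.1 mg/ml, i.e. 100 µg/ml (Protocol Summary; sections 6.1.2.1 and 6.1.2.2). Na-APR-1 doses are 10, 30 and 100 µg; the Na-GST-1 dose is 100 µg. There are six Groups of 10, with 5 saline and 5 Na-GST-1 subjects each, and three vaccinations per subject. GLA-AF is supplied at 25 µg/ml (section 6.1.2.3) and given at 5 µg.

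**Reproducing the plan's volumes** (volume = dose ÷ concentration):
- Na-APR-1: 10/100 = 0.1 ml, 30/100 = 0.3 ml, 100/100 = 1.0 ml. The first two agree with section 5.3.2 and the third with section 6.1.2.1.
- Na-GST-1: 100/100 = 1.0 ml, as stated.

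**Assumption for GLA-AF.** The mixing volumes are left to the Investigator's Brochure, which is not at hand. If 5 µg is added undiluted, it contributes 5/25 = 0.2 ml. Section 6.1.2.4 does not say whether the matched volume includes it, so both readings are shown.

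| Group | Na-APR-1 / GLA-AF (µg) | Saline, antigen volume only (ml) | Saline, with assumed 0.2 ml GLA-AF (ml) | Na-GST-1 (ml) | Na-GST-1 ÷ saline, two readings |
|---|---|---|---|---|---|
| 1 | 10 / 0 | 0.1 | 0.1 | 1.0 | 10; 10 |
| 2 | 10 / 5 | 0.1 | 0.3 | 1.0 | 10; 3.3 |
| 3 | 30 / 0 | 0.3 | 0.3 | 1.0 | 3.3; 3.3 |
| 4 | 30 / 5 | 0.3 | 0.5 | 1.0 | 3.3; 2 |
| 5 | 100 / 0 | 1.0 | 1.0 | 1.0 | 1; 1 |
| 6 | 100 / 5 | 1.0 | 1.2 | 1.0 | 1; 0.83 |

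**Extent.**
- Antigen volume only: Groups 1-4 differ, 4 × 10 = 40 of 60 subjects (67%), and 40 × 3 = 120 of 180 vaccinations.
- With the assumed GLA-AF volume: Groups 1-4 still differ 2- to 10-fold, and Group 6 differs by 0.2 ml. That gives 50 of 60 (83%) and 150 of 180, although the Group 6 difference is small.
- Forty of 60 is therefore the minimum on either reading.

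**What each masking measure does.**
- Two injections for everyone: equalises number, not volume.
- Opaque tape: hides contents, not the amount delivered.
- Separate preparation and non-assessing vaccinators: limit what staff see and pass on, not what the subject perceives.

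**Outcomes exposed.** Section 9.1 and Table 2 (section 9.2.2) share nine solicited items: pain, tenderness, erythema, induration/swelling, fever, headache, nausea, myalgia and arthralgia. Table 2 grades six of them at least partly on interference with activity: pain, headache, nausea, myalgia, arthralgia and, in part, induration/swelling. Tenderness is graded on discomfort. Erythema and fever are graded by measurement alone. Laboratory and antibody outcomes are not affected.

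**The case against.** The strongest reply is that section 5.3.2 saw the volume difference and dealt with it: syringes are taped for that reason, doses are prepared out of sight, and vaccinators do not assess. That does cover visual identification of contents and the route from vaccinator to assessor. It leaves what the subject may feel.

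It can also be said that sections 5.3.2 and 6.1.2.4 do not contradict each other, since both rest the blind on two injections and neither promises equal volumes. This is correct. The problem is an instruction that works against the stated purpose, not two opposite statements.

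Next, each subject experiences only his or her own pair of injections. To decode it, the subject must notice the difference and know that Na-GST-1 is always 1.0 ml. The protocol text at hand is silent on both, so actual unblinding is not shown. This point stands in full.

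The route to bias is narrow. Section 9.2.2 classes every local reaction in the first 7 days as definitely related, so a guess cannot alter that attribution. Clinicians examine the injection sites. The comparison with Na-GST-1 alone uses historical data, which this blind does not protect. Sections 11.1 and 11.2 describe a mainly descriptive study with low power. All this limits the weight of the point without removing it.

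Finally, matching volume does not perfect the blind. Saline contains no aluminum, while 1.0 ml of Na-GST-1 carries about 400 µg. Section 2.1.10 gives local reactions in 7.6% to 16.7% for aluminum-adsorbed vaccines. A second-arm reaction could still hint at allocation in any Group.

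**Conclusion.** The point holds as a modest masking weakness that should be fixed. As written, second-arm volume differs by allocation in at least 40 of 60 subjects, 2- to 10-fold across both readings of the GLA-AF volume, and the listed measures do not equalise it. The 40 of 60 follows directly from the protocol's own volumes; only the 50 of 60 reading needs the assumed 0.2 ml of undiluted GLA-AF.

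These figures measure exposure to the mismatch. The size of any reporting bias cannot be computed from the protocol, and whether subjects would perceive the difference or know its meaning is an open assumption. The concern is confined to solicited reactions that rest on the subject's account, in the comparison by co-administration status. No confirmatory claim depends on it.

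**What to change.** Before first vaccination, reconcile section 6.1.2.4 with the subject blinding in section 5.3.2, so that in every Group the saline placebo matches the Na-GST-1 injection it stands in for, in volume and in syringe size. Add a matching line to the preparation instruction under section 6.2. Keep the tape, separate preparation and non-assessing vaccinators. No active product changes. The second-arm volume difference then becomes 0 ml in all six Groups; the possible aluminum cue remains.

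The cost is a one-sentence amendment and a larger inert injection for the 4 × 5 = 20 saline subjects in Groups 1-4: 0.9 ml more per dose in Groups 1-2 and 0.7 ml more in Groups 3-4, leaving GLA-AF volume aside. The extra saline is 10 × 3 × 0.9 + 10 × 3 × 0.7 = 27 + 21 = 48 ml. With the assumed GLA-AF volume it is 15 × (0.9 + 0.7 + 0.7 + 0.5) = 42 ml in Groups 1-4, less 5 × 3 × 0.2 = 3 ml in Group 6, or 39 ml net. No visit or procedure is added.
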